2 STUDY OBJECTIVES

2.1 Primary Objective

- To evaluate the virologic effect of a single administration of VRC01 plus 10-1074 on rebound plasma viremia in subjects undergoing sequential antiretroviral treatment interruptions.

2.2 Secondary Objective

- To evaluate the safety of a single dose VRC01 plus a single dose of 10-1074 in HIV infected individuals.

2.3 Exploratory Objectives

- To investigate whether a single dose of VRC01 and 10-1074 allows the development of anti-HIV immunity (i.e., cytotoxic T lymphocyte or other immune responses) following the first and second round of ATI
- To determine changes in markers of immune activation and exhaustion in B and CD4⁺ and CD8⁺ T cells
- To determine changes in the size of HIV reservoirs following the first and second round of ATI

3 STUDY DESIGN

3.1 Description of the Study Design ([Figure 1](#))

The trial is a randomized double-blind placebo-controlled study to examine the effect of single infusions of VRC01 and 10-1074 in HIV-infected individuals undergoing sequential antiretroviral treatment interruptions. Participants will be randomized 1:1 to treatment with VRC01 plus 10-1074 or normal saline placebo. Study staff and participants will be blinded to treatment assignments.

First ATI

The day following study enrollment, subjects will stop ART (Day 0). Subjects taking non-nucleoside reverse transcriptase inhibitors (NNRTIs) will switch to a protease or integrase inhibitor-based regimen at least 2 weeks prior to Day 0 to ensure that the washout period of antiretroviral agents is roughly equal. During this first ATI phase of the study, HIV ribonucleic acid (RNA) levels and CD4⁺ T cell counts will be monitored every 2 weeks until plasma viremia of ≥ 200 copies/mL is detected.

VRC01 plus 10-1074/ Placebo Treatment Phase

Within 14 days of the first reported plasma viremia value of ≥ 200 copies/mL, subjects will be randomized 1:1 to receive single sequential infusions of VRC01 and 10-1074 or 2 sequential infusions of saline placebo. All subjects will restart ART the day following their bNAb/placebo infusions.

Second ATI

After re-institution of ART, subjects will have plasma viremia measured every 4 weeks. Twelve weeks after achieving ART-induced viral suppression subjects will undergo a second analytical treatment interruption. Viral suppression is defined as a plasma viremia < 40 copies/mL.

Transient “blips” in plasma viral levels are allowed as long as blips are < 400 copies/mL and succeeding viral levels return to < 40 copies/mL on subsequent testing.

[figure not shown]
During this second ATI, plasma viremia and CD4⁺ T cell counts will be monitored every 2 weeks and subjects will restart ART if they meet one or more of the following criteria prior to reaching ATI week 16:

- A confirmed $> 30\%$ decline in baseline CD4⁺ T cell count or an absolute CD4⁺ T cell count < 350 cells/mm³ that is associated with a HIV RNA level > 40 copies/mL.

- A sustained (>4 weeks) HIV RNA level of >1,000 copies/mL
- Any HIV-related syndrome (e.g. acute retroviral syndrome, opportunistic infection)
- Pregnancy

Subjects who have not met criteria to restart ART by ATI Week 16 will restart ART if they have measurable viremia (>40 copies/mL). Subjects whose HIV RNA levels are below the limit of detection (<40 copies/mL) at ATI Week 16 may elect to continue on the ATI phase of the study and have their CD4⁺ T cell counts and HIV RNA levels monitored every 2 weeks until HIV RNA levels become detectable at which time they will restart ART.

Figure 1: Study Outline

3.2 Study Endpoints

3.2.1 Primary Endpoint

The time to meet criteria for restarting antiretroviral therapy (ART) following the second ATI.

3.2.2 Secondary Endpoints

The rate of occurrence of grade 3 or higher AEs, including SAEs, that, per standard criteria (see safety [Section 12.3.1](#)) are probably or definitely related to the test articles VRC01 and 10-1074.

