12.8 Halting Criteria for the Protocol

Halting the study requires immediate discontinuation of the study agents administered for all subjects and suspension of enrollment until a decision is made about whether or not to continue study agent administration.

The halting criteria (as determined by the study PI and IND sponsor secondary to aggregate data review) for this study include:

- Any SAE or grade 4 AE that is possibly, probably, definitely related to the study agent; OR
- Any safety issue that the study PI or IND sponsor determines should halt the study.

Any related AE that is \geq grade 3 (not including transient, subjective infusion-related symptoms such as malaise, fatigue, headache, chills) will be reviewed within 48 hours of site awareness, by the PI and IND sponsor medical monitor, to consider the need for halting the protocol.

The PI and/or CSO will determine if the study should be halted. In addition, the FDA or Data and Safety Monitoring Board (DSMB) may halt the study at any time following review of any safety concerns.

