14 STATISTICAL CONSIDERATIONS

Efficacy Analysis

The primary outcome is the time from the start of the second treatment interruption until the subject meets criteria to restart ART. The probabilities of remaining below restart criteria for different amounts of time will be displayed using Kaplan-Meier plots and compared using the log-rank test. Secondary analyses will compare time to other milestones such as VL>400 and VL>1,000.

Safety Analysis

The proportion of subjects with grade 3 or higher AEs will be computed in each arm, along with 95% exact confidence intervals using the Clopper/Pearson method. The between-arm difference in the proportion of subjects with an AE of grade 3 or higher will be compared using Fisher's exact test and its associated confidence interval obtained by inverting two 1-sided tests at alpha=0.025.

Sample Size

Using control data from another similar trial, we modeled the time T (in days) to meet restart criteria as a Weibull distribution with survival function $P(T>t)=\exp[-(\lambda t)^p]$, where $\lambda=\exp(-3.861)=0.021$ and $p=1.957$. From these parameters, we estimated the median time to meet restart criteria as 39.486 days in the control arm. We can express the treatment effect in terms of either the hazard ratio θ or the factor β by which treatment increases the median time to meet restart criteria; β and θ are related by $\beta=\theta^{-1/p}$.

Assuming 25 subjects per arm are followed for 180 days, nearly everyone in both arms would be expected to meet restart criteria by 180 days. Power for a 40%, 50%, and 60% reduction in hazard is approximately 44%, 69%, and 90%, respectively ([Table 2](#)). These hazard reductions correspond to 30%, 42.5%, and 60% increases in the median time to meet restart criteria. Therefore, power is approximately 90% if the bNAb increases the median time to meet restart criteria by 60% relative to the placebo arm.

Table 2. Power under different treatment effects, expressed as either reduction in hazard or percent increase in median time to meet restart criteria.

Reduction in hazard	% Increase in median time to meet restart criteria	Power
40%	30%	44%
50%	42.5%	69%
60%	60%	90%

In terms of safety, a sample size of 25 subjects in the bNAb arm provides approximately 93% probability of detecting at least one AE that occurs in 10% or more of the population.

Table 3. Probability that at least 1 of 25 people in the bNAb arm will experience an AE that occurs in at least 10% of the population.

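### The secondary safety endpoint (probably or definitely related grade 3 or higher AEs) has no planned analysis; Section 14 analyses all grade 3 or higher AEs instead

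*Combined protocol and SAP*

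**What the plan says.** **Endpoint.** Section 3.2.2 defines the secondary endpoint as "The rate of occurrence of grade 3 or higher AEs, including SAEs, that, per standard criteria" "are probably or definitely related to the test articles VRC01 and 10-1074". The Protocol Summary gives the same definition, so this is not a slip in one place. It is the only secondary endpoint, and it serves the only secondary objective, which is safety (Section 2.2).

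**Analysis.** The Safety Analysis paragraph of Section 14 reads: "The proportion of subjects with grade 3 or higher AEs will be computed in each arm", with Clopper-Pearson 95% intervals. The between-arm difference in the proportion of subjects "with an AE of grade 3 or higher will be compared using" Fisher's exact test, with an interval "obtained by inverting two 1-sided tests at alpha=0.025". Attribution and SAEs are not mentioned.

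**Causality.** Section 12.3.1 has five categories, and possibly related is separate from probably and definitely related. Section 12.3 has the investigator assess every AE from the first infusion onward for seriousness, severity and causality.

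**Halting.** One criterion in Section 12.8 is "Any SAE or grade 4 AE that is possibly, probably, definitely related to the study agent". Other related AEs of grade 3 or higher, apart from transient subjective infusion symptoms, "will be reviewed within 48 hours of site awareness, by the PI and IND sponsor medical monitor".

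**The concern.** An analyst who follows Section 14 reports a different quantity from the one that the protocol names as its secondary endpoint. An analyst who follows Section 3.2.2 has no method, no unit and no comparison to apply. Nothing in the plan says which result is the secondary safety result, so the choice could be made after the data have been seen.

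The choice affects the answer. An all-cause count includes background grade 3 or higher events in both arms. A count of related events depends on the investigator's attribution and on whether possibly related events are included. Both are legitimate summaries, but they are not interchangeable.

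A smaller problem is that Section 14 does not say what its between-arm interval estimates. With 25 participants per arm and few severe events expected, that decides whether the interval is usable.

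**Working it through.** **1. The plan's own safety figure.** Table 3 gives the probability of at least one event among 25, which is 1 − (1 − p)^25:

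| True AE frequency | Computed | Table 3 |
|---|---|---|
| 1% | 22.2% | 22% |
| 5% | 72.3% | 72% |
| 10% | 92.8% | 93% |

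Table 3 reproduces. It refers to an AE without grade or attribution, so it does not settle which definition is meant.

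**2. The definitions side by side.**

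| | Protocol Summary and 3.2.2 | Section 14 |
|---|---|---|
| Severity | Grade 3 or higher, including SAEs | Grade 3 or higher |
| Attribution | Probably or definitely related | None |
| Unit | Rate of occurrence | Proportion of subjects |
| SAE below grade 3 | Unclear | Not counted |

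No other section plans an analysis of the attributed endpoint. Section 12.4.1 provides for listings and frequency tables to the sponsor, which is not an analysis of the endpoint.

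**3. Where particular events would be counted.**
- Probably or definitely related, grade 3 or higher: in the endpoint, and in the Section 14 proportion, but not shown there separately.
- Possibly related, grade 4: outside the endpoint, inside the Section 14 proportion.
- Possibly related SAE below grade 3: outside both, although it meets the halting criterion quoted from Section 12.8.

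**4. Does the definition matter? An illustration with assumed rates.** Suppose that 30% of bNAb participants have a treatment-caused grade 3 or higher AE, and that background events occur independently at rate b in both arms. The bNAb risk is then 1 − (1 − 0.30)(1 − b). Power of a two-sided 5% Fisher test, 25 per arm:

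| Background b | bNAb risk | Power |
|---|---|---|
| 0 | 30% | 81% |
| 5% | 33.5% | 66% |
| 10% | 37% | 50% |
| 20% | 44% | 33% |

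The first row is what a related-only comparison would reach with perfect attribution. The other rows are the all-cause comparison. With a 20% treatment-caused rate, power is 38%, 33%, 25% and 15%. These rates are not in the documents; they show only that the two definitions can behave differently.

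**5. The interval.** At 0/25 the per-arm Clopper-Pearson upper limit is 1 − 0.025^(1/25) = 13.7%, which is finite and informative. For the between-arm interval, the two possible parameters differ:
- *Odds ratio, by inverting Fisher's conditional test.* 0/25 against 0/25 gives 0 to infinity. 1/25 against 0/25 gives a lower limit of 0.025/0.975 = 0.026 and no upper limit. 3/25 against 0/25 gives 0.42 to infinity.
- *Risk difference, exact unconditional.* This is always bounded. For 0/25 against 0/25, inverting the score statistic has its least favourable case at zero risk in the other arm, so (1 − d)^25 = 0.025 and d = 13.7%. The interval is about −13.7 to +13.7 percentage points.

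Sparse counts are plausible. Section 1.1.3 reports no SAEs or related grade 3 AEs among 33 recipients of 10-1074, and one related grade 3 AE in the Phase 2 VRC01 trials.

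**The case against.** The best defence is that Section 14 plans the more inclusive analysis. Every endpoint event of grade 3 or higher is inside the all-cause proportion, all SAEs go to the DSMB (Section 12.12), and this is a secondary endpoint in a 50-person exploratory phase 1 trial. All of that is true and limits the severity. It does not supply an estimate of the stated endpoint.

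It can also be said that the phrase about SAEs in Section 3.2.2 means SAEs within grade 3 or higher. That reading is possible, but then the plan should say that lower-grade SAEs are outside both definitions.

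Three stronger inferences are tempting, and the documents do not support them:
- *A possibly related grade 4 event could halt the trial and yet vanish from the safety results.* It would not vanish, because the Section 14 proportion counts it. For the same reason, a contrast between 0% and 4% (0/25 against 1/25) from reclassifying one such event does not arise in the planned table.
- *The halting rule contradicts the endpoint.* A rule triggered by single events during the trial may properly be broader than an end-of-study summary.
- *Section 14 reports an odds-ratio interval.* The words "its associated confidence interval obtained by inverting two 1-sided tests" allow that reading, since they attach to Fisher's test. But the sentence concerns a difference in proportions, and inverting two one-sided exact tests is also a way to construct a risk-difference interval. Only the failure to name the parameter and method can be faulted.

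Nor would zero events leave the plan with nothing to report, because the per-arm Clopper-Pearson intervals stay informative.

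**Conclusion.** The point holds as a mismatch between endpoint and analysis. The plan defines its secondary endpoint by attribution and never analyses it, the units differ, and lower-grade SAEs are not counted in the analysis. This rests on the text alone and is certain.

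Its size is moderate. No stated number is wrong, and no grade 3 or higher event is lost. What is missing is the pre-specified estimate of the related-event proportion. The power figures rest on assumed event rates, on independent background events and on perfect attribution; in practice blinded investigators may attribute some placebo-arm events to study agent. The point about the interval is one of clarity: its practical cost arises only if the odds-ratio reading is applied and an arm has zero events.

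The change should be made before unblinding. It implies no judgement on the halting rule.

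**What to change.** 1. Align the Protocol Summary, Section 3.2.2 and Section 14 on one unit: participants with at least one qualifying event, counted from the first infusion.
2. Keep the all-cause grade 3 or higher comparison between arms, and state that SAEs of any grade count.
3. Add one table by arm of related events, showing both the probably or definitely related set and the set that also includes possibly related events, each with Clopper-Pearson intervals. State which row is the secondary endpoint.
4. State that the between-arm 95% interval is for the risk difference, and name an exact unconditional method, for example inversion of two one-sided score tests at 0.025. Note that this interval and Fisher's p-value may occasionally disagree at the margin.

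The cost is wording and one extra table. Severity, seriousness and causality are already recorded for every AE under Section 12.3, so no new data are needed. Table 3 and the halting rule stay as they are.

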4 STUDY POPULATION

4.1 Recruitment Plan

Subjects will be recruited from existing cohorts of individuals participating in NIAID protocols 09-I-0030 and 02-I-0202 who meet the Inclusion/Exclusion Criteria. Additional local and regional recruitment will be done using direct mailing to infectious disease physicians, internet ad campaigns, social media outlets, print ads, and from local clinics via the NIAID patient recruitment contract with Matthews Media Group.

4.2 Subject Inclusion Criteria

1. 18-65 years of age.

2. HIV-1 infection and clinically stable.
3. General good health and has an identified primary health care provider for medical management of HIV infection and is willing to maintain a relationship with a primary health care provider for medical management of HIV infection while participating in the study.
4. CD4⁺ T cell count >450 cells/mm³ at screening.
5. Documentation of continuous ART treatment with suppression of plasma viral level below the lower limit of quantification (LLOQ) for the assay used for ≥ 2 years. Individuals with “blips” (i.e., detectable viral levels on ART) prior to screening may be included provided they satisfy the following criteria:
 - a. The blips are <400 copies/mL, and
 - b. Succeeding viral levels return to levels below the limit of detection on subsequent testing.
6. Laboratory values within pre-defined limits at screening:
 - a. Absolute neutrophil count >1,000/mm³.
 - b. Hemoglobin levels >10.0 g/dL for men and >9.0 g/dL for women.
 - c. Platelet count >100,000/mm³.
 - d. Estimated or a measured glomerular filtration rate >60 mL/min/1.73 m² as determined by the NIH Clinical Center (CC) laboratory.
 - e. AST and alanine transaminase (ALT) levels of <2.5 x upper limit of normal (ULN), direct bilirubin within the normal range for the NIH CC laboratory.
7. Willingness to have samples stored for future research.
8. Willingness to undergo ATI
9. Willingness for both male and female subjects to agree to use barrier protection methods or abstinence during the ATI phase of the study to decrease the risk of HIV transmission.

Reproductive Risks

Contraception: The effects of VRC01 and 10-1074 on the developing human fetus are unknown. For this reason, men and women of childbearing potential must agree to use adequate pregnancy prevention. This includes the use an effective method of contraception (i.e. condom with spermicide, diaphragm with spermicide, hormone-eluting IUD, hormone-based contraceptive with condom) for the study duration. Subjects should also agree to use a male or female condom while off ART. Pregnancy prevention must be practiced continuously for the duration of study participation. Females of childbearing-age must have a negative pregnancy test result prior to receiving the infusions of VRC01 and 10-1074/placebo. During the course of the study, if a female subject, or the partner of a male subject suspects or in fact becomes pregnant, the affected subject should inform the study staff immediately, as well as the woman’s primary care physician.

4.3 Subject Exclusion Criteria

1. Chronic hepatitis B, as evidenced by a positive test for hepatitis B surface antigen (HBsAg), or chronic hepatitis C virus (HCV) infection, as evidenced by a positive test for HCV RNA. Subjects with a positive test for HCV antibody and a negative test for HCV RNA are eligible.
2. HIV immunotherapy or HIV vaccine(s) received within 1 year prior to screening.
3. Any prior history of receiving 10-1074 or VRC01.
4. Any licensed or experimental non-HIV vaccination (e.g., hepatitis B, influenza, pneumococcal polysaccharide) received within 2 weeks prior to study enrollment.
5. Receipt of other investigational study agent within 28 days of enrollment.
6. Any active malignancy that may require systemic chemotherapy or radiation therapy.
7. Systemic immunosuppressive medications received within 3 months prior to enrollment (Exceptions: [1] corticosteroid nasal spray or inhaler; [2] topical corticosteroids for mild, uncomplicated dermatitis; or [3] oral/parenteral corticosteroids administered for non-chronic conditions not expected to recur [length of therapy ≤10 days, with completion in ≥30 days prior to enrollment]).
8. History or other clinical evidence of:
 - a. Significant or unstable cardiac or cerebrovascular disease (e.g., angina, congestive heart failure, recent stroke or myocardial infarction).
 - b. Severe illness, malignancy, immunodeficiency other than HIV, or any other condition that, in the opinion of the investigator, would make the subject unsuitable for the study.
9. Active drug or alcohol use or any other pattern of behavior that, in the opinion of the investigator, would interfere with adherence to study requirements.
10. Pregnancy or breast-feeding at time of screening.
11. Documented multiclass antiretroviral drug resistance that, in the judgment of the investigator, would pose a risk of virologic failure should additional mutations develop during the study.

Co-enrollment Guidelines: Co-enrollment in other trials is restricted to observational studies or those evaluating the use of a licensed medication and is subject to approval of the principal investigator (PI).

4.4 Justification for Exclusion of Children (Special Populations)

Exclusion of Children:

Children are excluded from this study because there are insufficient data for adults regarding dosing of VRC01 and 10-1074 and AEs to judge the potential risk(s) in children.

4.5 Enrollment of NIH Employees

NIH employees and members of their immediate families may participate in this protocol. We will follow the Guidelines for the Inclusion of Employees in NIH Research Studies and will give each employee a copy of the “NIH information sheet on Employee Research Participation.”

For NIH employees:

- NIH staff may be a vulnerable class of subjects.
- Neither participation nor refusal to participate will have an effect, either beneficial or adverse, on the participant's employment or work situation.
- The NIH information sheet regarding NIH employee research participation will be distributed to all potential subjects who are NIH employees.
- The employee subject's privacy and confidentiality will be preserved in accordance with NIH CC and NIAID policies, which define the scope and limitations of the protections.
- For NIH employee subjects, consent will be obtained by an individual independent of the employee's team. Those in a supervisory position to any employee and co-workers of the employee will not obtain consent.
- The importance of maintaining confidentiality when obtaining potentially sensitive and private information from co-workers or subordinates will be reviewed with the study staff at least annually and more often if warranted.

5 STUDY AGENT/INTERVENTIONS

5.1 Regimen

10-1074 (30 mg/kg) and VRC01 (40 mg/kg) or matching placebos will be administered intravenously as single sequential infusions given at the end of the first ATI period (see [Figure 1](#)).

5.1.1 Formulation, Packaging and Labeling

10-1074 is provided by MassBio in single-use vials containing 30 mL of 10-1074 at a 20 mg/mL concentration.

VRC01 is provided by the VRC Pilot Plant operated by Leidos Biomedical Research, Inc., Frederick, MD, and is supplied at a concentration of 100 mg/mL. Two fill volumes are available, 2.25 ± 0.1 mL in a 3 mL glass vial and 6.25 ± 0.1 mL in a 10 mL glass vial.

Study agent vials will be individually labeled with the name of the material, volume, lot number, concentration, storage instructions, Investigational Use Statement ("Limited by Federal Law to Investigational Use"), and manufacturer information.

10-1074 should be stored at 2 - 8°C. Each vial is single use only. Partially used vials or solutions must not be used to prepare another dose and instead should be handled for destruction according to CC Pharmacy regulations for the disposal of biological agents.

The VRC01 product label designates the long-term storage temperature as -35°C to -15°C. Clinical site storage in a qualified, continuously monitored, temperature-controlled freezer with temperature excursions between -45°C and -10°C is acceptable. Following thaw, vials of VRC01 may be stored for up to 24 hours at controlled room temperature (maximum 27°C) and/or up to 4 weeks at 2°C to 8°C. Product may not be stored in direct sunlight. If stored at 2°C to 8°C, vials must be equilibrated at controlled room temperature (maximum 27°C) for a minimum of 30 minutes and may be held at room temperature for up to 8 hours prior to product preparation.

The site pharmacist must promptly report any storage temperature deviations outside of the normal allowance for the storage device to the PI and the investigational new drug (IND) Sponsor. The product must be quarantined in a separate area. The IND Sponsor's authorized representative will notify the site pharmacist if continued clinical use of the product is acceptable.

